## **5.6 Baseline Laboratory Values**

Descriptive statistics will be provided for baseline laboratory values for TSH and thyroglobulin for the OITT and ITT populations. In addition, TSH baseline values (mUI/L) will also be summarized by frequencies and percentages of subjects in the following categories for the same populations.

- $\leq 0.1$  mUI/L
- $0.1 - < 0.5$  mUI/L
- $\geq 0.5$  mUI/L

## **6 TREATMENTS AND MEDICATIONS**

### **6.1 Prior Non-Radiation Anticancer Therapy**

Prior non-radiation anticancer therapies will be coded per World Health Organization drug dictionary (WHO-DD).

The following will be summarized categorically or with descriptive statistics as appropriate for all subjects in the OITT, ITT, O-Safety and Safety population:

- Indication (disease under study, other)

- Therapy type (systemic, local, unknown, other)
- Context of therapy (neoadjuvant, adjuvant, locally advanced or metastatic setting)
- Number of prior systemic non-radiation anticancer regimens for DTC per subject (0, 1,  $\geq 2$ ) and descriptive statistics
- Number of prior VEGFR-TKI agents for DTC per subject (0,1,  $\geq 2$ ) and descriptive statistics
- Number of prior PD-1/PD-L1 agents (0,1,  $\geq 2$ ) and descriptive statistics
- Received either sorafenib or lenvatinib for prior treatment of DTC (Yes, No)
- Received prior sorafenib for DTC (Yes, No)
- Duration on sorafenib for DTC (< 1 month, 1 - <3 months, 3 - <6 months,  $\geq 6$  months) and descriptive statistics
- Received prior lenvatinib for DTC (Yes, No)
- Duration on lenvatinib for DTC (< 1 month, 1 - <3 months, 3 - <6 months,  $\geq 6$  months) and descriptive statistics
- Number of subjects receiving sorafenib only for DTC
- Number of subjects receiving lenvatinib only for DTC
- Received prior sorafenib and lenvatinib for DTC(Yes)
  - Received sorafenib before receiving lenvatinib
  - Received lenvatinib before receiving sorafenib
- Best response on the most recent regimen for DTC
- Descriptive summaries in months for the time from progression on most recent non-radiation anti-cancer regimen for DTC to randomization
- Descriptive summaries in months for the time from the end of most recent non-radiation anti-cancer regimen for DTC to randomization
- Number of subjects with progression while receiving sorafenib or lenvatinib for DTC at any time
- Number of subjects with progression of disease while receiving sorafenib or lenvatinib as most recent anti-cancer treatment for DTC

- Descriptive summaries in months for the time from progression on sorafenib or lenvatinib as the most recent non-radiation anti-cancer agent for DTC to randomization
- Number and percent of subjects who progressed on the most recent prior VEGFR-TKI therapy for DTC (Yes, No)
- Descriptive summary for total duration of treatment in months on prior VEGFR-TKIs for DTC
- Categorical summaries for total duration of treatment in months on prior VEGFR-TKIs for DTC as follows:
  - $< \text{median}$ ,  $\geq \text{median}$
- Descriptive summaries in months for the time from the end of most recent VEGFR-TKI therapy for DTC to randomization
- Descriptive summaries in months for the time from progression on most recent VEGFR-TKI therapy for DTC to randomization
- Categorical summaries for time from progression on the most recent VEGFR-TKI therapy for DTC to randomization
  - $\leq 3$  months
  - $> 3$  months
- Reason for stopping the most recent anti-cancer agent for DTC (progression, toxicity, completion, other)

All prior non-radiation anticancer agents will be summarized categorically by Anatomical Therapeutic Chemical (ATC) Class Text and WHO-DD base substance preferred name by treatment arm and type of therapy (Local, Systemic, Unknown) for all subjects in the OITT, ITT, O-Safety and Safety populations.

## **6.2 Prior Radiation Therapy**

Data obtained from the history of radiation therapy CRF will be summarized categorically or with descriptive statistics as appropriate for all subjects in the OITT, ITT, O-Safety and Safety populations:

- Number of prior radiation therapies for DTC per subject (1, 2,  $\geq 3$ ) and descriptive statistics

- Subject incidence of radiation therapy by indication (Disease under study and Other)
- Subject incidence of radiation therapy type (External beam radiation therapy [EBRT], Internal radiation therapy [Brachytherapy], Radioisotope therapy) received for DTC or Other indications
- Subject incidence of site type (Bone, Soft-tissue, Systemic, Unknown) of radiation received for DTC or Other indications
- Number and percent for anatomic sites that received radiation
- Descriptive summaries for time in months from the end of most recent radiation therapy for DTC to randomization

### **6.3 Prior Radioactive-Iodine Therapy**

The number of subjects who have previously received radioactive iodine or radioisotope therapy will be summarized. The number of subjects deemed ineligible for radioactive-iodine (RAI) therapy and the same deemed refractory to RAI therapy will be summarized. The reason for considering the subject refractory to or ineligible for RAI therapy will also be tabulated. Descriptive statistics for the time the subjects were deemed to be refractory to or ineligible for RAI therapy to randomization will also be provided. Categorical summaries will also be provided for number of subjects < median time from RAI refractory status to randomization and  $\geq$  median time from RAI refractory status to randomization. Descriptive statistics will also be provided for time from end of prior RAI therapy to randomization. All summaries will be provided for the OITT, ITT and O-Safety and Safety populations. A data listing will also be provided.

### **6.4 Prior and Concomitant Medications (Excluding Anticancer Therapy)**

Medications recorded on the CRFs will be coded using the WHO-DD. Prior and concomitant medications, other than prior and subsequent anticancer therapies, will be summarized by treatment group in the Safety population by ATC and WHO-DD base substance preferred name. In addition, prior medications will also be summarized in the O-ITT, ITT and O-Safety populations by ATC and WHO-DD base substance preferred name. Anticancer therapies are addressed in Sections 6.8 and 6.9 of this plan.

### **6.5 Study Treatment Exposure**

Study treatment exposure will be summarized with descriptive statistics in the O-Safety and Safety populations as follows.

Definition of duration (in days) of exposure per subject, including dose holds per subject, is defined in the table below:

| Treatment: | Cabozantinib   |  |  | Placebo  |
|-------------------|---|--|--|---|
| Group:     | Subjects randomized to and receiving cabozantinib (Cabozantinib arm) | Subjects randomized to placebo but receiving cabozantinib after crossover (Placebo crossover arm) | All subjects receiving cabozantinib including crossover subjects (All Cabozantinib arm) | Subjects randomized to and receiving placebo (Placebo arm) |
| Start Date | Date of 1 st dose of cabozantinib                                | Date of 1 st dose of cabozantinib after crossover   | Date of 1 st dose of cabozantinib   | Date of 1 st dose of placebo                           |
| End Date   | Date of decision to discontinue final cabozantinib (blinded/open-label)     | Date of decision to discontinue open-label cabozantinib  | Date of decision to discontinue final cabozantinib (blinded/open-label)                        | Date of decision to discontinue blinded placebo                   |

- Duration of exposure in months is defined as (duration of exposure in days as calculated above/30.4375)
- Average daily dose per subject (mg/day) of study treatment, calculated as (total dose in mg received / (duration of exposure in days))
- Percent dose intensity per subject calculated as  $100 * (\text{average daily dose mg/day}) / (60 \text{ mg/day})$
- Duration (in months) of exposure per subject, excluding dose holds defined, as (duration of exposure in days – total number of days with 0 mg of dose received during this interval) /30.4375

## 6.6 Study Treatment Modifications

Treatment modifications (holds and reductions) for study treatment will be summarized in the O-Safety and Safety populations. Only modifications due to AE, and protocol-defined dose levels, will be summarized.

The following summaries will be presented:

i. For dose reductions due to AE

Categorical summaries for:

- Number of subjects with any dose reduction
- Number of subjects who received each dose level
- Categorization of subjects by:
  - Lowest non-zero dose level received
  - Last non-zero dose level received
  - Last dose level received (including dose holds)

Descriptive statistics for:

- Number of dose reductions per subject
- Duration of treatment in months for each dose level (60 mg, 40 mg, 20 mg, 0 mg), defined for each subject as (cumulative number of days treatment was taken at each dose level) / 30.4375
- Time from first dose to first dose level reduction (first receipt of 40mg) (days) – amongst those who ever received 40mg
- Time from first dose to second dose level reduction (first receipt of 20mg) (days) - amongst those who ever received 20mg

ii. Summaries for dose holds due to AE:

- Descriptive statistics for number of dose holds (0mg dose level) due to an AE
- Descriptive statistics for duration of total and each dose hold per subject due to an AE, calculated as (stop date of hold – start date of hold + 1)
- Categorical summary for subjects with duration of holds due to an AE that can be classified as any number of days,  $\geq 7$  days,  $\geq 14$  days, and  $\geq 21$  days
- Descriptive statistics for time to first dose hold, time to first dose hold that was  $\geq 7$  days,  $\geq 14$  days, and  $\geq 21$  days. The time to dose hold is calculated as (start date of the hold – first dose date + 1)
- Descriptive statistics for time to second dose hold, time to second dose hold that was  $\geq 7$  days,  $\geq 14$  days, and  $\geq 21$  days

iii. Summaries for dose modifications (defined as a reduction or hold) due to AE:

- Frequency counts and percentages for subjects with any dose modifications
- Descriptive statistics for number of dose modifications (0-3)
- Descriptive statistics for time to the first dose modification
- Descriptive statistics for time to the second dose modification

## **6.7 Study Treatment Non-Compliance and Dosing Errors**

Treatment non-compliance and dosing errors for reasons other than AE will be summarized in the O-Safety and Safety populations. Frequency counts and percentages will be presented by treatment groups for:

- Subjects with dose hold (0 mg) due to non-compliance
- Subjects who received dose > maximum allowed dose level at any time (overdose)
- Subjects who received non-protocol specified dose level (< maximum allowed dose level) at any time due to subject non-compliance due to reasons other than AE, site/logistic error or other reason
- Subjects who received wrong dose ( $\leq$  maximum allowed dose level) at any time due to subject non-compliance due to reasons other than AE, site/logistic error or other reason

## **6.8 Non-Protocol Anticancer Therapy**

For the purpose of supporting safety evaluations:

Concomitant (see definition in Section 4.7.) non-radiation NPACT will be summarized by ATC text and WHO Drug base substance preferred name in the O-Safety and Safety populations.

For the purpose of supporting efficacy evaluations:

Concomitant and subsequent (see definition in Section 4.7.) NPACT, including radiation therapy, will be summarized by treatment group in the OITT and ITT populations as follows:

- Based on the non-radiation therapy received subjects will be categorized into one or more of the following categories: systemic, local, or unknown and all NPACTs falling under these categories will be summarized by ATC text and WHO Drug based substance preferred name
- Time to first systemic NPACT will be summarized by descriptive statistics
- Frequency counts and percentages will be presented for radiation therapy indication, type and site

## **6.9 Post-randomization Radiotherapy, Surgery/Procedure**

Post-randomization radiation therapy and surgery/procedures that impacted the target lesion(s) (Yes, No, Unknown) will be summarized by treatment group for subjects in the OITT, ITT, O-Safety and Safety populations.

## **6.10 Concomitant Transfusions**

Concomitant transfusions will be summarized by transfusion type and treatment group for subjects in the O-Safety and Safety populations.

## **7 CROSSOVER BASELINE CHARACTERISTICS**

The following descriptive summaries will be provided for the placebo subjects in the ITT population who crossover to receive cabozantinib upon confirmed radiographic progression and also for the cabozantinib subjects who continue on study drug beyond progression:

- Number of subjects receiving open-label cabozantinib
- Age
- Frequency counts and percentages of ECOG status at the assessment immediately prior to crossover or receipt of open-label cabozantinib
- Time to progression while on randomized study treatment
- Number of target lesion locations prior to crossover per Investigator's assessment (including thyroid)
  - 1
  - 2
  - $\geq 3$

## **8 EFFICACY ANALYSES**

The multiple primary efficacy endpoints for this study are duration of PFS and ORR per BIRC. Formal hypothesis tests are planned for these endpoints. Data as described in Section **Error! Reference source not found.** will be considered.

### **8.1 Primary Efficacy Endpoints**

## **8.1.1 Objective Response Rate (ORR)**

### **8.1.1.1 Definition**

For each subject, best overall response (BOR) is defined as the best tumor assessment category as determined per RECIST 1.1 that occurs through the first overall timepoint response of PD and prior to any of the censoring events defined for the primary analysis of PFS as described in Section 8.1.2. Tumor assessment categories are ranked as: confirmed complete response (CR), confirmed partial response (PR), stable disease (SD), progressive disease (PD) and not evaluable (NE). To be classified as confirmed CR or confirmed PR, confirmation must have occurred on a subsequent visit that is  $\geq 28$  days after the response was first observed. To be classified as SD, at least one overall timepoint response of SD must be documented  $\geq 49$  days after randomization.

The ORR is defined as the proportion of subjects with a BOR of confirmed CR or confirmed PR.

### **8.1.1.2 Primary Estimand**

The difference in proportions between treatment conditions in subjects in ORR (best overall response of confirmed complete or partial response) per RECIST 1.1 in the targeted patient population:

- irrespective of whether the assigned study treatment was given
- irrespective of clinical deterioration
- irrespective of whether local radiation was given to bone
- irrespective of surgical resection of non-target lesions
- irrespective of receipt of local non-protocol anti-cancer medications other than for disease under study
- prior to any surgical resection of target tumor lesions
- prior to receipt of systemic non-protocol anti-cancer medications
- prior to receipt of local non-protocol anti-cancer medications for disease under study
- prior to receipt of local radiation to soft tissue for disease under study
- prior to loss to radiographic follow-up
- prior to death

Derived as follows:

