### *Bone lesions*

- Bone scan, PET scan or plain films are not considered adequate imaging techniques to measure bone lesions. Computed tomography or MRI must be used to corroborate findings by these modalities.
- Lytic bone lesions or mixed lytic-blastic lesions, with identifiable soft tissue components, that can be evaluated by cross-sectional imaging techniques such as CT or MRI can be considered as measurable lesions if the *soft tissue component* meets the definition of measurability described above.
- Blastic bone lesions are non-measurable.

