### *Lesions with prior local treatment*

- Lesions situated in a previously irradiated area are not considered measurable.

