**Table 5: Primary Estimand Attribute for ORR**

| Estimand attribute  | Primary definition for study  |                     |
|---------------------------------|---|---------------------|
| Population                      | Subjects randomized into the study intended to include patients with radioiodine-refractory differentiated thyroid cancer who have progressed after prior VEGFR-targeted therapy. |                     |
| Endpoint                        | Radiographic response per RECIST 1.1  |                     |
| Intercurrent events             | Event   | Strategy            |
|                                 | Receipt of assigned study treatment   | Treatment policy    |
|                                 | Receipt of local radiation to bone  | Treatment policy    |
|                                 | Surgical resection of non-target tumor lesions  | Treatment policy    |
|                                 | Death   | Treatment policy    |
|                                 | Loss to radiographic follow up  | Treatment policy    |
|                                 | Receipt of local non-protocol anti-cancer medications other than for disease under study  | Treatment policy    |
|                                 | Surgical resection of target tumor lesions  | While on treatment* |
|                                 | Receipt of systemic non-protocol anti-cancer medications  | While on treatment* |
|                                 | Receipt of local non-protocol anti-cancer medications for disease under study   | While on treatment* |
|                                 | Receipt of local radiation to soft tissue for disease under study   | While on treatment* |
| Population summary              | Difference in proportions of subjects with a best overall response of confirmed complete response or confirmed partial response per RECIST 1.1 between treatment conditions.      |                     |
| Estimator                       | Fisher's exact test   |                     |

 See Appendix E for estimand terminology

\* A modified version of the “while on treatment” strategy is employed for these intercurrent events. Only data prior to the occurrence of these intercurrent events is of interest, but under the ITT principle, receipt of study treatment itself is not considered.

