#### 8.1.2.4 Primary Definition

For the primary analysis directed toward the primary estimand, duration of PFS is defined as the time from randomization to the earlier of either the date of radiographic progression per BIRC or the date of death due to any cause.

$$\text{PFS (months)} = (\text{earliest date of progression, death, censoring} - \text{date of randomization} + 1) / 30.4375$$

General censoring rules for the primary analysis of PFS are described below, with details provided in Table 8(analysis ID PFS-EP-1):

- Subjects who receive systemic NPACT, or local NPACT for disease under study, or non-protocol radiation therapy for disease under study (other than to bone) or surgery to resect target lesions before experiencing an event will be right censored at the date of the last ATA on or prior to the date of initiation of subsequent therapy/surgery. If there is no such tumor assessment after randomization, the subject will be right censored on the date of randomization.
- Subjects who have not experienced an event (and are not otherwise censored) at the time of data cutoff will be right censored on the date of their last tumor assessment after randomization that is on or prior to the data cutoff. If there is no such tumor assessment after randomization, the subject will be right censored on the date of randomization.
- Subjects who miss two or more ATAs (operationally defined as an interval of 126 days in the first year and 196 days after the first year without an ATA) followed by an event (progression or death) will be right censored on the date of their most-recent ATA prior to the missing assessments. If there is no such tumor assessment after randomization, the subject will be right censored on the date of randomization.

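### The primary ORR and PFS rules ignore radiation to bone even when the irradiated bone lesion is a target lesion, and no sensitivity analysis covers this.

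*Combined protocol and SAP*

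**What the plan says.** **ORR.** SAP 8.1.1.2 defines response "irrespective of whether local radiation was given to bone", and Table 5 gives the strategy as "Receipt of local radiation to bone | Treatment policy". By contrast, only data "prior to receipt of local radiation to soft tissue for disease under study" and "prior to any surgical resection of target tumor lesions" count. SAP 8.1.1.1 cuts best overall response at the first PD or at a PFS censoring event, so scans after bone radiation stay in.

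**PFS.** SAP 8.1.2.2 and Table 6 also put bone radiation under treatment policy. SAP 8.1.2.4 censors at "non-protocol radiation therapy for disease under study (other than to bone"), and protocol 9.2.2.2 has the same exemption.

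**Which lesions can be targets.** Protocol Appendix H normally lists bone lesions as nonmeasurable, but admits "Lytic bone lesions or mixed lytic-blastic lesions, with identifiable soft tissue components" if the soft-tissue part meets the size criterion. Target lesions are drawn from all measurable lesions, up to two per organ and five in total.

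**What is recorded.** SAP 6.9 tabulates "Post-randomization radiation therapy and surgery/procedures that impacted the target lesion(s) (Yes, No, Unknown"), by arm. The tabulation feeds into no endpoint.

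**The concern.** For surgery, the SAP asks whether a target lesion was affected: resection of a non-target lesion is ignored, and resection of a target lesion closes the window. For radiation it asks only which tissue was treated. Soft-tissue radiation for the disease under study therefore ends follow-up even if no target lesion was touched, while radiation to a bone lesion whose diameter enters the sum of diameters changes nothing.

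A target lesion that shrinks because it was irradiated lowers the sum of diameters for a reason unrelated to study treatment. That can help a subject reach PR, or offset growth elsewhere and postpone target-lesion PD. The ORR test is sensitive to single subjects, because it uses 100 subjects at a two-sided 1% level and expects almost no placebo responses.

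**Working it through.** **1. Tracing the rule.**

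| Event before PD | Target lesion affected? | ORR (Table 5) | PFS (Tables 6 and 8) |
|---|---|---|---|
| Resection | yes | window ends | censored |
| Resection | no | ignored | ignored |
| Soft-tissue radiation, disease under study | yes or no | window ends | censored |
| Bone radiation | yes or no | ignored | ignored |

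Only the last row keeps using a target lesion after it has been treated locally.

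**2. Looking for an analysis that would catch it.** Table 7 keeps treatment policy for bone radiation in both alternative PFS estimands. Tables 8 and 9 omit events that are treatment policy under all estimands, so bone radiation has no row there. Table 10 reclassifies other kinds of censored subjects. SAP 8.1.1.5 changes the assessor and the population for ORR, not this rule. Nothing covers it.

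**3. Reproducing the plan's ORR power.** Inputs from SAP 2.4: 100 subjects, 2:1, two-sided 0.01, 2% against 35%, pooled variance. The formula gives 93.7% with 33.3 and 66.7 subjects, and 93.5% with 33 and 67. Both agree with the stated value of more than 90%. The planned primary test is Fisher's exact test (SAP 8.1.1.4). Enumerating all outcomes for 67 and 33 (an assumed exact 2:1 split) and rejecting when p < 0.01 with the cabozantinib rate higher gives 97.0%.

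**4. Leverage of one placebo response (conditional).** Smallest significant cabozantinib count out of 67:

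| Placebo responders of 33 | Needed on cabozantinib | Fisher p |
|---|---|---|
| 0 | 12 | 0.0077 |
| 1 | 16 | 0.0096 |
| 2 | 19 | 0.0095 |
| 3 | 23 | 0.0074 |

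Power = Σ over y of P(Y = y) × P(X ≥ threshold for y), with Y ~ Bin(33, 0.02) and X ~ Bin(67, 0.35).

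- P(Y = 0, 1, 2, 3) = 0.513, 0.346, 0.113, 0.024.
- P(X ≥ 12, 16, 19, 23) = 0.999, 0.982, 0.899, 0.591.
- As planned: 0.513×0.999 + 0.346×0.982 + 0.113×0.899 + 0.024×0.591 + small terms = 97.0%.
- With one spurious response added to every placebo count, each y takes the threshold for y + 1: 0.513×0.982 + 0.346×0.899 + 0.113×0.591 + small terms = 89.1%.

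The loss is 96.96 − 89.13 = 7.8 points, given that such a response occurs. If its probability were 1% to 5% (an assumption; the documents give none), the expected loss would be 0.01×7.8 to 0.05×7.8, or about 0.1 to 0.4 points.

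**5. What a spurious PR requires.** PR needs a 30% fall in the sum of diameters. If the irradiated lesion makes up a share s of the baseline sum and shrinks by a fraction r, it contributes s×r. A sole target lesion must shrink by 30%; one making up 40% of the sum must shrink by 75% to reach PR unaided. The response must also be confirmed at least 28 days later, without new lesions or non-target PD.

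**The case against.** The best counter-argument is that the situation will be rare. Protocol 7.1.2 says that local treatment with impact on tumor lesions, palliative radiation included, should wait until radiographic progression, with an exception for clinically unavoidable cases after consulting the sponsor. Radiation after PD per BIRC affects neither endpoint. What remains is a discouraged event in an uncommon type of target lesion. This limits the size of the problem, but the exception has no analysis rule.

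Radiation to such a lesion might also be coded as soft tissue, in which case the existing rules apply. The SAP does not say how a bone lesion with a soft-tissue component is classified. The imaging and BIRC charters may deal with irradiated target lesions, but they are not among the documents. The SAP 6.9 table would at least make such cases visible.

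Three stronger readings are tempting and are not supported:

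- *The SAP contradicts Appendix H.* The statement "Lesions situated in a previously irradiated area are not considered measurable" stands under a heading on prior local treatment, and protocol 5.7.6.5 sends prior radiation history to the BIRC for target selection. It does not govern lesions irradiated on study.
- *The bias has a known direction.* No passage shows that bone radiation before progression is commoner on placebo. A spurious response or delayed PD on placebo works against cabozantinib; on cabozantinib it works in favor. Shrinkage also lowers the nadir, which can bring later PD forward.
- *The power loss is an expected loss.* It assumes that one spurious placebo response has occurred.

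**Conclusion.** The gap is real. As written, the primary rules keep counting a target lesion after local radiation if the lesion lies in bone, in contrast with the SAP's own handling of target-lesion resection, and no planned analysis tests the consequence.

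The effect is probably small. The documents give no rate of post-randomization radiation to target bone lesions. The 27% and 38% with bone metastases in the two cited phase 3 trials, and the 84% in the cited previously treated phase 2 cohort, describe any bone metastasis rather than measurable bone targets irradiated before PD. The drop from 97.0% to 89.1% rests on the 67 and 33 split, the design rates, and one spurious placebo response taken as given. It shows leverage, not likelihood. The case for acting is that the rule is inconsistent on a primary endpoint and the item needed to repair it is already planned for summary.

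**What to change.** Revise the SAP before unblinding:

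- In Tables 5, 6 and 7, limit the treatment-policy row to local bone radiation that does not impact a target lesion, and align the lists in 8.1.1.2 and 8.1.2.2.
- In Tables 8 and 9, add a row for radiation impacting a target lesion, bone included, handled in each column as target-lesion resection is handled. These tables have no bone-radiation row now, so this is an addition. Give Tables 5 to 7 the matching row.
- Align 8.1.2.4, and record the departure from protocol 9.2.2.2 as a change to planned analyses under SAP 4.9.
- Identify the subjects from the item summarized in SAP 6.9, and state in advance how Unknown is treated.
- Keep the current rule as a sensitivity analysis for ORR and PFS.

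The cost is a SAP revision and programming, with no new data. The downside is that a few more subjects are censored or have a shorter response window. That censoring may be informative, since a need for palliative radiation can signal worsening disease, which is a further reason to report both versions.
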